At Baseline (Day 1), eligible subjects will be assigned to the treatment arms using permuted block randomization stratified by NASH CRN Fibrosis stage (2 or 3) and presence or absence of documented T2DM (yes or no). Eligible subjects will be randomized 2:1 to one of the following 2 treatment arms and will receive the same treatment for the duration of the study:

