Subjects who are newly randomized in Part 2 of the study will complete the following visits: At Baseline (Day 1) eligible subjects will be randomized to treatment using permuted block randomization, and presence or absence of documented T2DM (yes or no). Newly enrolled subjects will be randomized 2:1 to one of the following 2 treatment arms to achieve a total of approximately 2000 randomized subjects in study (of which up to 1200 subjects will have been randomized in Part 1 and 800 in Part 2):

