**Table 9–1 Treatment Arms: Part 1 and Part 2**

Arm	Part 1 N	Part 2 Newly Randomized Subjects N	Part 2 Total Subjects (Randomized in Part 1 or Part 2) N	Treatment
A	800	534	1334	CVC 150 mg, once daily
B	400	266	666	Placebo, one daily

Subjects who remain in Part 1 of the study at Month 12 will continue their previously assigned blinded treatment from Part 1 into Part 2 and will continue to be evaluated in Part 2. In addition, new eligible subjects will be enrolled into Part 2 and randomized after the enrollment for Part 1 is completed. This will result in a total of approximately 2000 subjects in Part 2 (including up to 1200 subjects who were randomized in Part 1); approximately 1334 subjects treated with CVC and 666 subjects treated with placebo.

In Parts 1 and 2, CVC and placebo will be administered as double-blinded study drug. Study drug (CVC or placebo) must be taken once daily with food.

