Analysis of the primary endpoint of Part 2 will use the logrank test, stratified by randomization strata (fibrosis stage [2 vs 3] and presence or absence of T2DM at Baseline, for a total of 4 strata), to compare the rates in the 2 randomized treatment arms. If multiple adjudicated events are observed in a single subject, only the first observed event will be used in the analysis. The analysis will use the mITT analysis set, with supportive analyses reported for the ITT and PP2 analysis sets. Subjects who do not have an adjudicated event will be censored for analysis at the last recorded study visit. The p-value for the test of no difference between treatment arms (hazard ratio=1) will be presented as well as the hazard ratio from a proportional hazards model (CVC divided by placebo) and corresponding 95% CI. To manifest strong evidence from a single confirmatory study, the hypothesis test of clinical endpoint will be performed at a significance level of 0.00125 (2-sided) if the test of the surrogate endpoint is successful and 0.00005 (2-sided) otherwise. For study success, the hypothesis test of clinical endpoint will be performed at a significance level of 0.05 (2-sided) if the test of the surrogate endpoint is successful and 0.002 (2-sided) otherwise.

Analysis of secondary efficacy endpoints of Part 2 will use similar methods to the primary endpoint analysis in Part 2. The primary endpoint in Part 1, improvement in fibrosis by at least one stage and no worsening of steatohepatitis at Month 12, will be reported for subjects not in the Part 1 analysis (subjects newly randomized in Part 2), and for all subjects in the study (Month 12 results from Part 1 and Part 2 combined). Results for the mITT and PP2 analysis sets will be reported for the secondary endpoints in Part 2. Binary endpoints will be analyzed with the CMH procedure, stratified by randomization strata. Continuous endpoints will be analyzed with analysis of covariance, with randomization strata included as covariates. Time to event endpoints will be analyzed with the stratified logrank test, stratified by randomization strata.

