Subjects who progress to cirrhosis or reach an adjudicated liver-related clinical outcome will complete the study and return to the clinic for a Follow-up visit (Visit 98) 30 days after the last dose of study drug. After completion of the Follow-up visit (Visit 98), subjects will become eligible for open-label access to CVC in a separate study (Clinical Study Protocol 3152-201-002).

Part 1

At Baseline (Day 1), eligible subjects will be assigned to the treatment arms using permuted block randomization stratified by NASH CRN fibrosis stage (2 or 3) and presence or absence of documented type 2 diabetes mellitus (T2DM) (yes or no). Eligible subjects will be randomized 2:1 to one of the following 2 treatment arms:

Arm	N	Treatment
A	800	CVC 150 mg, once daily
B	400	Placebo, once daily

All subjects will undergo safety assessments at the Baseline visit and at Months 1, 3, 6, 9, and 12. The liver biopsy, used to evaluate the efficacy endpoints, must be performed within ± 2 weeks of the Month 12 visit (Visit 7).

Part 2

In Part 2, Baseline (Day 1) eligible subjects will be randomized to treatment using permuted block randomization, stratified by presence or absence of documented T2DM (yes or no). Newly enrolled subjects will be randomized 2:1 to one of the following 2 treatment arms to achieve a total of approximately 2000 randomized subjects in Part 2 (of which approximately 1200 subjects will have been randomized in Part 1):

Arm	Newly Randomized Subjects in Part 2 N	Total Subjects (Randomized in Part 1 or Part 2) N	Treatment
A	534	1334	CVC 150 mg, once daily
B	266	666	Placebo, once daily

Subjects who enter Part 2 from Part 1 of the study will have study visits every 3 months until Part 2 is completed. Study drug will be dispensed and adverse events (AEs), concomitant medications, and adherence to study drug will be reviewed at every visit (every 3 months). Safety laboratory assessments will be performed every 6 months through the end of the study.

Subjects who are randomized in Part 2 and who did not participate in Part 1 of the study will undergo safety laboratory assessments at Months 1, 6, and 12 and every 6 months thereafter through the end of the study. Beginning at Month 3, AEs, concomitant medications, and adherence will be reviewed every 3 months through the end of the study.

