
Part 2: Primary efficacy endpoint (time-to-event)
	
Time-to-event analyses will be performed using the Kaplan-Meier product-limit method with tabular and graphical presentation for the cumulative probability of event rate by treatment group. Subjects will be censored for analysis at the last recorded study visit.
 
Analysis of the primary endpoint of Part 2 will use the logrank test, stratified by true fibrosis stage (2, 3) and T2DM status (presence, absence) at baseline, for a total of 4 strata, to compare the rates in the 2 randomized treatment arms. If multiple adjudicated events are observed in a single subject, only the first observed event will be used in the analysis. The analysis will use the mITT analysis set, with supportive analyses reported for the
	
Same as above
	
Time-to-event KM figure

Type of Endpoint	Description	Timing	Methodology
Part 2 (Global/Region-specific Europe): Testing (primary endpoint) (time-to-event)	
ITT and PP2 analysis sets. Subjects who do not have an adjudicated event will be censored for analysis at the last recorded study visit. The p-value for the test of no difference between treatment arms (hazard ratio=1) will be presented as well as the hazard ratio from a proportional hazards model (CVC divided by placebo) and corresponding 95% CI.
 
Global/Region-specific Europe: To manifest strong evidence from a single confirmatory study, the hypothesis test of clinical endpoint will be performed at a significance level of 0.00125 (2-sided) if the test of the surrogate endpoint is successful and 0.00005 (2-sided) otherwise. For study success, the hypothesis test of clinical endpoint will be performed at a significance level of 0.05 (2-sided) if the test of the surrogate endpoint is successful and 0.002 (2-sided) otherwise.
		
Part 2: Primary efficacy endpoint (sensitivity analyses 1)	The primary endpoint will be performed using the ITT and PP1 populations as sensitivity analyses.	Same as above	Same as above
Part 2: Primary efficacy endpoint (sensitivity analysis 2)	An assessment of primary endpoint will also be made using multiple imputation with informative censoring imputation model. Refer to Section 5.1.1.1.5.	Same as above	Multiple imputation with informative censoring imputation model

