Part 2: Primary efficacy endpoint (sensitivity analysis 3)	Analysis of the primary endpoints for Part 2 will also use the Cochran-Mantel-Haenszel (CMH) test, stratified by true fibrosis stage (2, 3) and T2DM status (presence, absence) at baseline, for a total of 4 strata, to compare the event rates in the 2 randomized treatment arms.	Same as above	Cochran-Mantel-Haenszel (CMH) test, stratified by true fibrosis stage (2, 3) and T2DM status (presence, absence) at baseline
Part 2: Primary efficacy endpoint (sensitivity analysis 4)	An assessment of primary endpoint will also be made using imputation of subjects censored without an event before 5 years of follow-up	Same as above	Time-to-event Logrank test

Type of Endpoint	Description	Timing	Methodology
Part 2: Secondary efficacy endpoints (binary)	
Analysis of secondary efficacy endpoints of Part 2 will use similar methods to the primary endpoint analysis in Part 2. The primary endpoint in Part 1, improvement in fibrosis by at least one stage and no worsening of steatohepatitis at Month 12, will be reported for subjects not in the Part 1 analysis (subjects newly randomized in Part 2), and for all subjects in the study (Month 12 results from Part 1 and Part 2 combined).
 
Results for the mITT and PP2 analysis sets will be reported for the secondary endpoints in Part 2. Binary endpoints will be analyzed with the CMH procedure, stratified by true fibrosis stage (2, 3) and T2DM status (presence, absence) at baseline.
	Same as above	Cochran-Mantel-Haenszel (CMH) test, stratified by true fibrosis stage (2, 3) and T2DM status (presence, absence) at baseline

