6.1 Study Treatment Conventions

Treatment assignment will be done using permuted block randomization via IxRS stratified by NASH CRN fibrosis stage (2 or 3) and presence or absence of documented T2DM (yes or no). In case of discordance of the assignment of randomization strata between IxRS and EDC, the true fibrosis stage and T2DM status at baseline will be used for the analysis.

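### Pooled Part 2 analyses merge newly randomised Stage 3 subjects with Part 1 Stage 3 subjects and have no term for Part; adding it costs nothing and recovers a little power if the cohorts differ materially in risk

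*Protocol*

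**What the plan says.** **Part 1 randomisation.** Protocol 7.1.1 and 9.2.7 and SAP 4.1.1 agree on "permuted block randomization stratified by NASH CRN Fibrosis stage (2 or 3) and presence or absence of documented T2DM (yes or no". That gives four cells.

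**Part 2 randomisation.** Protocol 9.1 says that "new eligible subjects will be enrolled into Part 2 and randomized after the enrollment for Part 1 is completed". Inclusion criterion 4 limits these subjects to Stage 3. Protocol 7.1.2 says that "eligible subjects will be randomized to treatment using permuted block randomization, and presence or absence of documented T2DM (yes or no", and 9.2.8 is worded alike. The word for stratification has dropped out of the protocol sentence, but SAP 4.1.1 supplies it: "randomized to treatment using permuted block randomization, stratified by presence or absence of documented T2DM (yes or no". The SAP's summary of changes attributes this to a change in stratification under protocol amendment 4.

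**SAP 6.1.** This section describes a single scheme and does not distinguish the Parts: "Treatment assignment will be done using permuted block randomization via IxRS stratified by NASH CRN fibrosis stage (2 or 3", together with T2DM.

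**Analysis.** Protocol 12.3.2.2 stratifies the Part 2 log-rank test by "randomization strata (fibrosis stage [2 vs 3] and presence or absence of T2DM at Baseline, for a total of 4 strata". SAP Table 5-14 has it "stratified by true fibrosis stage (2, 3) and T2DM status (presence, absence) at baseline, for a total of 4 strata". SAP Table 5-2 gives the Cox model the same two factors. The Part 2 CMH analyses also use them, including the Month 12 report "for all subjects in the study (Month 12 results from Part 1 and Part 2 combined". No analysis has a term for Part.

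**The concern.** The two Stage 3 cohorts are enrolled one after the other and are not handled identically. SAP Table 5-4 takes the end of follow-up as about 96 months for Part 1 subjects and 84 for new ones. SAP Table 5-19 has first-year laboratory visits at Months 1, 3, 6, 9 and 12 in Part 1, but at Months 1, 6 and 12 for new subjects. That can shift when a MELD score of 15 or more is detected.

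If the underlying hazard also differs between the cohorts, a stratum that merges them mixes two baseline hazards. The log-rank statistic is then pulled somewhat towards no effect. This is the trial's clinical-outcome test. At the strict level of 0.00125 its planned power is 85%, so there is little to spare. Part is known at randomisation and could be used at no cost.

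**Working it through.** **Inputs from the documents.** Protocol 12.8.2: hazard ratio 0.62, 367 events, 2000 subjects at 2:1, two-sided alpha 0.00125 and 0.05, stated power 85% and 99%, and 80% of placebo subjects event-free. SAP 5.2.1: 1293 subjects in Part 1 and about 707 new ones (originally 1200 and 800).

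**Assumptions, not in the documents.** Exponential event times; Stage 3 hazard twice that of Stage 2; half the subjects with T2DM and no effect of T2DM on risk; 400 to 900 Stage 3 subjects in Part 1; and the hazard ratio between the two Stage 3 cohorts.

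**1. The plan's own figure.** Schoenfeld's formula with 2:1 allocation gives Z = √(367 × 2/9) × |ln 0.62| = 9.031 × 0.478 = 4.317.
- At 0.00125: Φ(4.317 − 3.227) = 86.2%.
- At 0.05: Φ(4.317 − 1.960) = 99.1%.

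Both agree with the stated 85% and 99%.

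**2. Four against six strata.** Both tests were run on the same simulated trials: 15,000 per row, 2:1 permuted blocks within cell, hazard ratio 0.62 in every cell, 600 Part 1 Stage 3 and 800 new subjects. Average event counts were about 350 to 385. The gain column is therefore the one to read, not the absolute power. Gains are taken before rounding.

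| Hazard, new vs Part 1 Stage 3 | Power, 4 strata | Power, 6 strata | Gain, points (SE) |
|---|---|---|---|
| 1.0 | 91.71% | 91.67% | −0.05 (0.04) |
| 1.25 | 91.08% | 91.15% | +0.07 (0.05) |
| 1.5 | 90.81% | 91.09% | +0.27 (0.06) |
| 2.0 | 89.23% | 89.89% | +0.67 (0.09) |
| 3.0 | 87.24% | 89.30% | +2.06 (0.12) |
| 0.5 | 91.37% | 91.89% | +0.52 (0.08) |

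- With 70% of events seen only at biopsy, the gains are +0.5, +0.9 and +2.3 at 1.5, 2 and 3.
- With 400 or 900 Part 1 Stage 3 subjects, or the 1293/707 split, they are about +0.2 at 1.5 and +0.6 to +0.7 at 2.
- At alpha 0.05 the change is at most about 0.2 points.

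**3. In terms of events.** The ratio of mean Z (4 strata over 6) is 4.606/4.625 = 0.996 at 1.5, 4.523/4.575 = 0.989 at 2, and 4.412/4.539 = 0.972 at 3. One minus the squared ratio is the information lost: 0.8%, 2.3% and 5.5%, or about 3, 8 and 20 of 367 events. Applied to Z = 4.317, the 86.2% becomes 85.8%, 85.1% and 83.4%. This shortcut overstates the loss a little, because the 4-stratum statistic also varies less (SD 1.044 against 1.055 at twofold).

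**4. Type I error.** With no treatment effect and a twofold cohort difference (10,000 trials), rejection in the upper tail at 0.025 was 2.35% with 4 strata and 2.45% with 6.

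**5. Pooled Month 12 CMH.** The assumed rates of 15% and 25% imply an odds ratio of (0.25/0.75)/(0.15/0.85) = 1.89. Asymptotic power at 0.0012 was compared for different placebo response rates in Part 1 Stage 3 and new Stage 3 subjects. The gain from 6 strata is 0.01 points at 15% vs 12%, 0.1 at 15% vs 10%, 0.3 at 25% vs 10%, and 0.6 to 0.8 at 15% vs 5%.

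**The case against.** A reader might infer that the trial has six documented randomisation strata and that the protocol's count of four is an error. The documents do not go that far. Nothing says that Part 2 has its own randomisation list, and SAP 6.1 describes one scheme. In a Stage 3-only cohort, stratifying by T2DM gives the same two cells as stage by T2DM, so the four analysis strata cover every factor named in either scheme. The SAP also analyses by true stage and T2DM status where these disagree with IxRS, so it does not claim to follow the randomisation cells. This stands. What remains is that Part is a known pre-randomisation factor left out of the analysis, and that SAP 6.1 does not match SAP 4.1.1.

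It is also fair to say that no risk difference is documented. Eligibility differs only in the stage allowed, and central reading and the Month 12 and Month 60 biopsies are shared. Different follow-up lengths are handled by censoring and risk sets. The limit of 600 centres applies to the whole study, and nothing ties added sites to Part 2. The laboratory difference is two first-year visits and bears on one component. All of this stands, which is why the size above is a range over assumptions and not an estimate.

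Finally, two prespecified prognostic factors are a legitimate choice of strata. That is so; the case for adding Part is only that it costs nothing and may help.

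**Conclusion.** The point holds as a low-severity improvement. The pooled Part 2 analyses ignore the enrolment cohort, which causes no bias and no inflation of type I error. The power lost at 0.00125 is nil for like cohorts, under about 1 point up to a twofold hazard difference in either direction, and about 2 points at threefold. These figures rest on the assumptions listed with the calculation.

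Two stronger readings should be resisted:
- **That power is given away whenever the cohorts differ in risk, or that the planned 85% is in danger.** At a hazard ratio of 1.25 the gain is within simulation error. Only a threefold difference takes the plan's figure clearly below 85%, and nothing in the documents suggests one.
- **That the pooled Month 12 result is compromised.** It is a reported secondary analysis. The alpha allocation in SAP 5.1.1.3.3 covers only the surrogate and clinical outcome endpoints, and the loss is below 1 point in the cases tried.

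**What to change.** Before Part 2 unblinding:

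1. In Protocol 12.3.2.2 and SAP Tables 5-2 and 5-14, stratify the Part 2 log-rank test by Stage 2, Stage 3 randomised in Part 1, and Stage 3 newly randomised in Part 2, each by T2DM (6 strata). Carry the same grouping into the Cox model and, for consistency, into the pooled Month 12 and Month 60 CMH analyses. Because the SAP uses true stage, say where a newly randomised subject whose true stage proves to be 2 is placed.
2. Leave the Part 1 analysis at 4 strata.
3. Reconcile SAP 6.1 with Protocol 7.1.2 and 9.2.8 and SAP 4.1.1, and state whether Part 2 used its own randomisation list.

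**Cost.** The power cost is nil within simulation error (−0.05 to +0.01 points when the cohorts are alike). Part is already held, since it defines the Part 1 analysis. Strata stay large: if half of Part 1 is Stage 3 and half of all subjects have T2DM, the Stage 3 strata hold about 1293/4 = 323 and 707/2 = 354 subjects. The real cost is procedural, because the four strata are written into the protocol's primary analysis and the change has to be documented there as well as in the SAP.

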**Table 7–2 Treatment Arms in Part 2**

Arm	Randomized Subjects in Part 2 N	Total Subjects (Randomized in Part 1 or Part 2) N	Treatment
A	534	1334	CVC 150 mg, once daily
B	266	666	Placebo, once daily

Study drug will be administered as double-blinded treatment and must be taken once daily with food.

Newly enrolled subjects in Part 2 will undergo safety laboratory assessments at Months 1, 6, and 12 and every 6 months thereafter through the end of the study. Beginning at Month 3, AEs, concomitant medications, and adherence will be reviewed every 3 months through the end of the study.

Newly enrolled subjects will undergo a liver biopsy at Screening for assessment of eligibility and a second post-treatment liver biopsy will be collected within  $\pm 2$  weeks of the Month 12 visit. All subjects (newly randomized subjects with a liver biopsy diagnosis of NASH and Stage 3 liver fibrosis [by NASH CRN system] and those who continue from Part 1) will undergo a liver biopsy at Month 60 (within  $\pm 2$  weeks) after the first dose of study drug.

Subjects who permanently discontinue study drug before planned end of study are encouraged to complete all subsequent study visits and participate (without treatment) in Part 2 of the study for assessment of clinical outcomes (at the discretion of the investigator, subjects who permanently discontinue study drug may be followed every 6 months unless otherwise specified by the protocol).

Subjects who undergo early termination from the study will return to the clinic within 48 hours for an Early Discontinuation visit and will return to the clinic for a Follow-up visit 30 days after the last dose of study drug.

Survival data will be collected for all study subjects at the end of the study.

Subjects who progress to cirrhosis or reach a liver-related clinical outcome, which must be adjudicated by an independent adjudication committee, will complete the study and return to the clinic for a Follow-up visit 30 days after the last dose of study drug (Visit 98). After completion of the Follow-up visit (Visit 98), these subjects will become eligible for open-label access to CVC in a separate study (Clinical Study Protocol 3152-201-002).

### Key Assessments

During Part 2 of the study

- Screening will only be required for newly enrolled subjects and will not be required for subjects continuing their previously assigned blinded treatment from Part 1. A Screening visit is to occur within 3 months before the Baseline visit for any new subjects to be enrolled in Part 2. The informed consent and patient education materials about NASH, liver fibrosis, liver biopsy procedures, and study retention tools will be reviewed at the Screening visit for newly enrolled subjects.
- As part of Screening, assessment of serum laboratory tests (hematology and chemistry panels), serum hepatic fibrosis indices (including FIB-4, APRI, and NFS) and evaluation of liver stiffness via TE or liver imaging (performed no more than 6 months prior to the first day of Screening at sites where available) should be performed to aid in identifying subjects with clinically significant liver fibrosis prior to proceeding with a new liver biopsy.
- A historical liver biopsy, obtained no more than 6 months prior to the first day of Screening, that meets protocol-required specifications or a new liver biopsy will be evaluated for all subjects as part of Screening to confirm histologic evidence of NASH and fibrosis Stages 2 or 3.
- Subjects newly enrolled in Part 2 meeting all other eligibility criteria and with suspicion of significant liver fibrosis (through clinical evaluation, hepatic fibrosis indices, and/or liver stiffness assessment [performed no more than 6 months prior to the first day of Screening]) will undergo a new liver biopsy during the Screening period. Newly randomized subjects in Part 2 will undergo a further liver biopsy at Month 12 (within  $\pm 2$  weeks). A liver biopsy will be performed at the Month 60 visit ( $\pm 2$  weeks) for all subjects.
- Fasting metabolic parameters, including lipid panel (triglycerides, total cholesterol, HDL, LDL, VLDL), glucose, insulin, and HbA1c, will be measured at Baseline for newly randomized subjects and every 6 months through the end of study for all subjects.
- Samples for biomarkers of systemic inflammation, including IL-1 $\beta$ , IL-6, hs-CRP, and fibrinogen, will be collected at Baseline for newly randomized subjects and every 6 months through the end of the study for all subjects.

- Samples for non-invasive serum hepatic fibrosis indices (FIB-4, APRI, NFS), Liver Stiffness, ELF Score, and PRO-C3 every 12 months for all subjects
- At selected sites where available, non-invasive assessment of liver fibrosis by TE will be performed at Baseline (if not performed at Screening) for newly randomized subjects and annually through the end of the study for all subjects.
- Weight, waist circumference, and hip circumference will be performed at Screening and Baseline for newly randomized subjects and every 6 months through the end of the study for all subjects. Height will be performed at Screening.
- Physical examinations, vital signs, and laboratory analyses (serum chemistries and hematology) will be performed at Screening, Baseline, Months 1, 6 and 12 for subjects who are newly randomized in Part 2, and every 6 months thereafter through the end of the study for all subjects. Serum IgG, ANA, anti-SMA, and anti LKM 1 and anti-LC1 antibodies will be evaluated at Baseline for subjects newly randomized in Part 2. Electrocardiograms will be performed at Baseline for newly randomized subjects and annually through the end of the study for all subjects.
- Clinical outcomes, AEs and concomitant medications will be assessed at each study visit.
- An ultrasound exam to screen for hepatocellular carcinoma (HCC) and presence of ascites will be performed at Month 60.

